13.1 Extent of Exposure

The following exposure and compliance parameters will be summarized descriptively by treatment:

- Total number of days exposed, defined as date of last dose of study drug date of first dose of study drug + 1.
- Number of doses administered, calculated from the subject dose diary and the in-clinic
 dosing data. If a subject is exposed to study drug for more than 1 day, and returns no
 diary records, then the total number of doses is regarded to be missing. Otherwise, for
 any day for which there is no diary record, it is assumed that no study drug was
 administered at home.
- Grams (g) of study drug administered, total and average per day. Drug administered is calculated as the summation of the difference between dispensed weight and returned weight for all returned tubes. Unreturned/unopened tubes will be assumed unused and will be included as 0 gram in amount drug used calculation.
- Percent compliance will be calculated as the (Number of Doses Administered) / (Number of Days Exposed) * 100.
- Subject compliance, defined as ≥80% compliance while enrolled in the study. If the percentage of study medication compliance cannot be computed, the subject is assumed to be less than 80% compliant.

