4.7 Lost to Follow-Up

A subject is considered lost to follow-up if he/she repeatedly fails to return to the study site for scheduled visits and is unable to be contacted by the study site. The following actions must be taken if a subject fails to return to the clinic for a required study visit:

- The site must attempt to contact the subject or caregiver and reschedule the missed visit as soon as possible, counsel the subject on the importance of maintaining the assigned visit schedule, and ascertain whether or not the subject wishes to and/or should continue in the study.
- Before a subject is deemed lost to follow-up, the Investigator or designee must make every effort to regain contact with the subject or caregiver (where possible, 3 telephone calls and, if necessary, a certified letter to the subject's last known mailing address or local equivalent methods). These contact attempts should be documented in the subject's medical record.
- Should the subject or caregiver continue to be unreachable, he/she will be considered to have withdrawn from the study with a primary reason of lost to follow-up. In this case, the discontinuation date will be listed as the date the certified letter was mailed to the subject.

5 Study Treatment

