5.4 Compliance with Study Drug Administration

At Baseline, study staff will provide the subject or caregiver with detailed instructions concerning protocol requirements and use of study drug. Additionally, subjects or caregivers will be asked to complete a daily diary with the time of each application of study drug, except on study visit days. At each post-Baseline study visit, study staff will review use of study drug, as applicable, with the subject or caregiver. Subject compliance will be assessed via study diary completion.

When subjects are dosed at the site, they and/or their caregiver will apply the study drug under supervision of the study staff. The date and time of each dose administered in the clinic will be recorded in the source documents. The study drug and study subject identification should be confirmed at the time of dosing by a member of the study site staff other than the person dispensing the study drug.

At the time of dispensing study drug to each subject, site personnel will weigh the tubes to be dispensed with the cap on and will record the weight of all tubes dispensed at each visit in the drug accountability logs. Subjects and/or caregivers will be instructed to bring all used and unused tubes with them to each study visit. Site personnel will weigh the returned tubes (used and unused) with the cap on and record the weight in the drug accountability logs. If a tube has been lost, discarded, or forgotten by the subject, then the site personnel will make a notation of this on the drug accountability logs. Forgotten tubes should be returned by the subject at the next study visit. Tubes of study medication dispensed at the most recent prior visit which remain unopened (the foil cap on the tube remains fully intact/undisturbed) may be re-dispensed to study subjects at the current visit. Unopened tubes may only be re-dispensed once. Opened, partially used tubes or tubes with foil overlay removed are not to be re-dispensed to study subjects. If there is any question as to re-dispensation, sites should issue new tubes of study medication to the subject(s).

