5. DETERMINATION OF SAMPLE SIZE

It is estimated that the proportion of subjects who will achieve a vIGA-ADTM score of 0 or 1 and at least a 2-grade reduction from Baseline to Week 8 will be 45% for subjects receiving tapinarof compared with 25% for subjects receiving vehicle control, based upon the Phase 2 results. With 400 subjects randomized in a 2:1 ratio (267 subjects receiving tapinarof, and 133 subjects receiving vehicle control), this will provide 97.2% power for statistical significance (2-sided p <0.05). The power is calculated from a Fisher Exact sample size calculation. It is assumed that 15% of the subjects receiving tapinarof will be lost to follow-up by 8 weeks compared with 30% of the subjects receiving vehicle control. These subjects will be included in the primary analysis using the multiple imputation method.

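### Unreturned tubes are counted as 0 g used, so total grams of study drug can only be biased low (descriptive exposure summary; minor)

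*SAP*

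**What the plan says.** SAP 13.1 lists among the exposure parameters "Grams (g) of study drug administered, total and average per day". The derivation is: "Drug administered is calculated as the summation of the difference between dispensed weight and returned weight for all returned tubes". It continues: "Unreturned/unopened tubes will be assumed unused and will be included as 0 gram in amount drug used calculation". The denominator of the daily average is not stated. The nearest candidate is the first item in the same list, "Total number of days exposed, defined as date of last dose of study drug" minus the first dose date, plus 1.

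Protocol 5.4 has sites weigh every tube when dispensed and when returned, used or not. For tubes that do not come back, the accountability log carries an entry: "If a tube has been lost, discarded, or forgotten by the subject, then the site personnel will make a notation of this". The section adds: "Forgotten tubes should be returned by the subject at the next study visit". Protocol 6.6 asks that, at virtual visits, subjects be told to keep their empty tubes.

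SAP 5 and Protocol 10.2 plan on the assumption that "15% of the subjects receiving tapinarof will be lost to follow-up by 8 weeks compared with 30% of the subjects receiving vehicle control". Protocol 4.7 describes a subject lost to follow-up as one who "repeatedly fails to return to the study site for scheduled visits and is unable to be contacted by the study site".

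**The concern.** The rule puts two different states together. A returned unopened tube is a known zero, and the weight formula already gives about 0 g for it. The added sentence therefore acts mainly on tubes that never came back, where nothing in the documents supports zero. The protocol foresees that empty tubes may be thrown away, and those would be fully used.

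The same SAP section treats another gap differently. A subject exposed for more than one day who returns no diary has the number of doses set to missing, not to zero. (A single day without a record in a returned diary is counted as no home dose.)

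What is at stake is the description of how much cream was applied in a trial enrolling from age 2 years. Understated grams would make the safety results appear to have arisen at a lower applied amount than was really used.

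**Working it through.** **Direction.** Let u be the true grams used from an unreturned tube, with u ≥ 0. The rule records 0, so the error in a subject's total is minus the sum of u over unreturned tubes. That is zero or negative, never positive.

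**Plan figures.** The documents state no figure for grams. The one design figure beside the loss rates is the power of 97.2%. Full enumeration of the Fisher exact test (267 vs 133, 45% vs 25%, two-sided 0.05) gives 97.6%, which is close. It does not depend on the grams rule.

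**Illustration of size.** Inputs from the documents: tubes dispensed at Day 1 and Weeks 1, 2 and 4, so dispensing intervals of 7, 7, 14 and 28 days (56 in all); loss of 15% and 30%. Assumptions, not in the documents: constant daily use; day of loss equally likely from 1 to 56; use continues until loss; no Early Termination visit; the tubes last dispensed never come back; all other tubes are returned.

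- Mean days of use recorded as 0 g per lost subject: 4, 4, 7.5 and 14.5 in the four intervals, with weights 7/56, 7/56, 14/56 and 28/56. That is 0.5 + 0.5 + 1.875 + 7.25 = 10.125 days. The mean day of loss is 28.5.
- Tapinarof: true mean days 0.85 × 56 + 0.15 × 28.5 = 51.875. Unrecorded: 0.15 × 10.125 = 1.519. Bias: −1.519/51.875 = −2.9%.
- Vehicle: true mean days 0.70 × 56 + 0.30 × 28.5 = 47.75. Unrecorded: 0.30 × 10.125 = 3.038. Bias: −3.038/47.75 = −6.4%.

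**Other assumptions, total grams.**

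| Scenario | Tapinarof | Vehicle |
|---|---|---|
| Half of those lost return their tubes: 0.759/51.875; 1.519/47.75 | −1.5% | −3.2% |
| All lost on Day 29: 0.15/51.95; 0.30/47.9 | −0.3% | −0.6% |
| All lost on Day 55: 4.05/55.85; 8.1/55.7 | −7.3% | −14.5% |
| Base case, plus 5% of tube sets from attended intervals unreturned: 1 − 0.95 × 50.356/51.875; 1 − 0.95 × 44.713/47.75 | −7.8% | −11.0% |

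**Average grams per day (base case).** The result depends on the missing denominator.

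- True days of use: the mean shortfall among lost subjects is 100%, 34.1%, 32.4% and 31.6% by interval (1 minus the mean of interval start divided by day of loss). Weighted, this is 40.7%. Times 0.15 and 0.30: −6.1% and −12.2%.
- Days up to the last clinic dose: the shortfalls are 1/1, 1/8, 1/15 and 1/29, weighted 17.5%. Times 0.15 and 0.30: −2.6% and −5.2%.
- Only days covered by returned tubes: no bias.

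**The case against.** **Little depends on grams.** SAP 13 makes no formal safety comparisons. Compliance and its per-protocol criterion use doses and days. The plasma summaries in SAP 12.1 are broken down by age, race and %BSA and scaled by baseline %BSA, not by grams. This stands, and it sets the severity.

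**The protocol limits the problem.** Subjects bring all tubes to each visit, forgotten tubes come back at the next one, and the Early Termination visit collects study drug. This stands as a limit on size, not on direction.

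**Reporting of unreturned tubes cannot be ruled out.** The table and listing titles of SAP Appendix C are not in the text available, so a count of unreturned tubes may be planned there. The derivation in SAP 13.1 would be unchanged.

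**The slash might mean tubes that are both unreturned and unopened.** This does not help. The formula sums over returned tubes only, so an opened tube that stays out still contributes nothing.

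A reader might also infer more than the documents support:

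- That grams is the only quantitative measure of exposure. SAP 13.1 also gives days exposed, doses and compliance, and SAP 12.1 gives plasma concentrations in a subset. Grams is the only measure of amount applied.
- That unreturned tubes are mostly used ones, or that mean grams are low by 5% to 20%. No return rate or state of use is given, and such a range only restates an assumed share of tubes.
- That each 30 g tube costs 30/56 = 0.54 g/day. The 56-day denominator is not in the SAP.
- That a subject lost after Week 4 has 28 of 56 days wrongly set to zero. That is the extreme case. For a subject who stopped applying at Week 4, zero is right.

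**Conclusion.** Wrong as written, minor severity. The downward direction of total grams follows from the rule itself. The size does not: about 3% (tapinarof) and 6% (vehicle) holds only if all the planned loss to follow-up occurs without tube return and with use continuing until loss, and it roughly halves if half of those lost return their tubes.

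The difference between arms should not be over-read. The 15% and 30% are planning assumptions about follow-up, not tube-return rates. The difference vanishes if lost subjects applied nothing from their last tubes. The arm with the greater assumed loss is vehicle, which contains no tapinarof, so the figure that matters for exposure to the active drug is the smaller one. Nothing here bears on the primary analysis, the power, diary-based compliance or the per-protocol set.

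**What to change.** In SAP 13.1:

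1. Assign 0 g only to tubes confirmed unopened.
2. Treat unreturned tubes as unknown.
3. Report the number of unreturned tubes by arm.
4. Show total grams under both bounds: each unreturned tube counted as 0 g, and as fully used. The recorded weights are taken with the cap on and include the tube itself, so the upper bound should use the net content.
5. State the denominator of the daily average. As a supportive summary, give the average over dispensing intervals with all tubes returned. That summary favours subjects who attend, so it should not stand alone.

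The cost is a small derivation change, provided that the tube weights and the log notations required by Protocol 5.4 are available for analysis, which the documents do not confirm. Some subjects will have a range and not a single total.

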3.3 Definition of Study Completion and Eligibility for Open-Label, Long-Term Extension Study

In order to complete the study, a subject must complete 8 weeks of study assessments. To be considered a "study completer" in terms of treatment period, a subject must complete $\geq 80.0\%$ of the intended doses. The number of intended doses is defined as the Study Day of the subject's Week 8 visit minus 1 (e.g., if the subject's Week 8 visit occurs on Day 57, their number of intended doses is 56). To be eligible for the OL-LTE study, subjects must be a "study completer." Subjects who complete the study will have the option to enroll in the Phase 3 OL-LTE study of 48 weeks in duration. Details of that study are provided in a separate clinical trial protocol.

The end of study is defined as when the last active subject has completed the 8 weeks of assessments in this study and either enrolls in the OL-LTE study OR does not enroll in the OL-LTE study and completes the Week 9 (Follow-up) Visit.

4 Study Population

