8. ANALYSIS SETS

The safety population will be used for the safety analyses and will include all randomized subjects who receive at least 1 application of study drug. Treatment assignment will be based on the treatment received.

The following subject populations will be used for efficacy analyses:

- The intent-to-treat (ITT) population will include all randomized subjects. Treatment assignment will be based on the randomized treatment.
- The per-protocol (PP) population will exclude ITT subjects with protocol deviations or other events that may impact the interpretation of the primary efficacy endpoint, regardless of whether the deviation(s) is considered major or minor. Exclusion criteria for the Per-protocol population may include:
 - Failure to meet the enrollment inclusion/exclusion criteria
 - Specified use of prohibited concomitant medication

Systemic Agents:

- Oral/systemic corticosteroids for >5 days
- Oral PDE4 inhibitors used for atopic dermatitis (e.g., roflumilast, apremilast); or other conditions if not on stable dose for period prior to and over course of the study
- Any oral immunosuppressive medication including cyclosporine, Imuran (azathioprine), methotrexate, tacrolimus, any Janus kinase inhibitor
- Injected IL4/13 blocking biologic including lebrikizumab, dupilumab
- Oral/systemic retinoids (e.g., alitretinoin), if not on a stable dose for period prior to and over course of the study
- Other injected monoclonal antibodies with potential impact on AD (omalizumab)
- Oral/systemic antihistamines for ≥ 3 days when used for skin conditions
- Oral/systemic antibacterials for ≥ 3 days when used for skin conditions
- Other investigational drug

Topical Agents:

- Topical immunomodulators on affected skin (other than transient <5
 days focal treatment for AESI) including topical corticosteroids, topical
 calcineurin inhibitors (Elidel, Protopic), topical PDE4 inhibitor
 (crisaborole/Eucrisa), coal car containing products
- Topical emollients containing keratolytics (including salicylic acid, urea) on affected skin (other than transient ≤7 days focal treatment for AESI)
- Topical antihistamines for ≥ 3 days when used for skin conditions
- Topical antibacterials limited to gentamicin and neomycin
- Other investigational drug
- Failure to be compliant with treatment regimen (compliance < 80%)
- Inclusion of scalp in efficacy assessment (see protocol section 5.1.5)

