9.2 Protocol Deviations

Major protocol deviations that could potentially affect the efficacy or safety conclusions of the study will be identified before database lock and unblinding of individual subject treatment information. Major protocol deviations may include, but are not limited to:

- Randomized subjects who did not satisfy selected inclusion and exclusion criteria;
- Subjects who received the wrong treatment or an incorrect dose;
- Subjects who received an excluded concomitant treatment;
- Failure to have a Week 8 assessment within ± 7 -day visit window;
- Non-compliance with the dosing regimen. A subject will be considered compliant with the dosing regimen if they applied ≥80% of the expected doses. Expected number of doses is based on length of time enrolled in the treatment-phase of the study.

Reasons for exclusion of a subject from the analysis and protocol violations (minor/major) will be listed.

All protocol deviations, including the deviation designation (major or minor), category, and indication of whether the deviation led to an exclusion of a subject from the PP population, will be presented in a data listing.

Protocol deviations will be summarized by deviation category and treatment group. In addition, COVID-19 related protocol deviations will be summarized separately.

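### SAP 13.1 computes compliance over first-to-last-dose days and SAP 9.2 over time enrolled in the treatment phase, so a subject who stops drug but stays enrolled can fall on either side of the 80% rule

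*SAP*

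**What the plan says.** Four places bear on the point.

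- **SAP 13.1, the formula.** "Percent compliance will be calculated as the (Number of Doses Administered) / (Number of Days Exposed) * 100". The denominator is defined just above it: "Total number of days exposed, defined as date of last dose of study drug date of first dose of study drug + 1" (the minus sign between the two dates was lost when the PDF was read).
- **SAP 13.1, the threshold.** "Subject compliance, defined as ≥80% compliance while enrolled in the study". This wording refers to enrolment, which the formula does not use.
- **SAP 9.2, protocol deviations.** Not applying at least 80% of expected doses is a possible major deviation, and "Expected number of doses is based on length of time enrolled in the treatment-phase of the study".
- **SAP 8, analysis sets.** Compliance below 80% is one possible reason for exclusion from the per-protocol set. The list opens with "Exclusion criteria for the Per-protocol population may include". It gives no compliance formula and no cross-reference.

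Protocol 3.3 has a related rule. It begins "The number of intended doses is defined as the Study Day of the" and goes on to take the Week 8 visit day minus 1. It uses 80% of that number to decide who counts as a study completer and may enter the extension study.

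**The concern.** Under 13.1 the denominator ends with the last application. Missed days before the last dose lower the score, but days after it do not count at all. Someone who doses daily and then stops scores 100% whenever that happens. Under 9.2 the days after the last dose still count while the subject remains in the treatment phase.

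One 80% threshold therefore rests on two denominators within the SAP. Because SAP 8 names neither, per-protocol membership for some subjects depends on which section is followed. 13.1 is the natural choice for a programmer, since it has the only explicit percent-compliance formula and a rule for when it cannot be computed. 9.2 is the natural choice for whoever classifies deviations. The per-protocol analysis repeats the primary and secondary endpoints, so its membership should not turn on an unstated choice.

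The SAP's revision history suggests how this arose: Version 2.0 took the enrolled-time sentences out of 13.1, while the same wording still stands in 9.2. The point rests on the current text of the two sections, not on that history.

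**Working it through.** **Inputs.** 13.1: doses / (last dose date − first dose date + 1). 9.2: doses / expected doses over time enrolled in the treatment phase. Threshold: 80%. Week 8 visit on Day 57 (Protocol schedule), with no study drug applied at that visit. The last supervised application is at Week 4, target Day 29.

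**The plan's own figure.** Protocol 3.3 says a Week 8 visit on Day 57 gives 56 intended doses: 57 − 1 = 56. For a subject dosing from Day 1 to Day 56, 13.1 gives 56 − 1 + 1 = 56 days exposed. For a full completer the denominators agree.

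**Stops drug, stays enrolled to Day 57.** Daily dosing to the last dose. The 9.2 denominator is taken as 56.

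| Last dose | 13.1 | 9.2 | 80% rule under 9.2 |
|---|---|---|---|
| Day 29 | 29/29 = 100% | 29/56 = 51.8% | fails |
| Day 42 | 42/42 = 100% | 42/56 = 75.0% | fails |
| Day 44 | 44/44 = 100% | 44/56 = 78.6% | fails |
| Day 45 | 45/45 = 100% | 45/56 = 80.4% | passes |

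0.80 × 56 = 44.8, so 45 doses are needed. The sections disagree for every last dose from Day 29 to Day 44. Earlier stops disagree more (Day 14: 14/14 = 100% against 14/56 = 25.0%), but they require that no later supervised clinic dose was applied.

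9.2 does not say exactly how days are counted. With 57 in place of 56 the range is 29/57 = 50.9% to 44/57 = 77.2%, which does not change the conclusion.

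**Stops drug and leaves the next day.** Last dose Day 14: 13.1 gives 14/14 = 100% and 9.2 gives 14/14 = 100%. There is no conflict.

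**Stops drug and leaves 14 days later (assumed gap).** 9.2 gives 14/28 = 50.0% for a last dose on Day 14 and 28/42 = 66.7% for Day 28. 13.1 gives 100% for both.

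**Gaps before the last dose.** 12 of 14 days gives 12/14 = 85.7% under 13.1, so 13.1 does register missed doses within the dosing period.

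**The case against.** The case against giving this much weight has several parts.

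- **The affected path may be uncommon.** Protocol 4.6.1 generally ties stopping drug to withdrawal, followed by an Early Termination visit. It lets subjects permanently off drug remain only for safety assessments, at discretion. The documents give no frequency for subjects who stop but attend Week 8. This stands: the number affected cannot be estimated.
- **Passing the compliance criterion does not by itself keep anyone in the per-protocol set.** The SAP 8 list is not binding, it extends to other events that affect interpretation, and membership is settled before unblinding. SAP 9.2 also names "Failure to have a Week 8 assessment within ± 7 -day visit window" as a possible major deviation. This stands in part, but a subject who stops around Day 29 to 44 and attends Week 8 on time does not trigger that deviation.
- **The estimand limits the damage.** The per-protocol analysis of the primary endpoint uses the MI estimand data, where stopping for an adverse event or lack of efficacy already counts as failure. This stands for those two reasons. A subject who stops for another reason, and uses no specified prohibited medication, keeps the Week 8 outcome.

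Three stronger readings are tempting but not supported.

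- A reader might infer that every early stopper passes under 13.1 and fails elsewhere. A subject who stops and leaves together scores about 100% under 9.2 too.
- A reader might infer that 13.1 contradicts Protocol 3.3. That rule governs completer status and extension eligibility, and it gives no denominator without a Week 8 visit.
- A reader might use the assumed 15% and 30% losses to argue that the per-protocol set is contaminated unequally by arm. Those figures are loss to follow-up, and the subjects at issue here attend Week 8.

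**Conclusion.** Wrong as written. SAP 13.1 does not match its own enrolment wording, and it conflicts with SAP 9.2 for subjects who stop applying drug while still enrolled in the treatment phase. For daily dosing to Day 29 to 44 with Week 8 on Day 57, the gap is 100% against about 52% to 79%, across the 80% line.

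This assumes a 9.2 denominator of 56, and that a subject who has stopped applying drug still counts as enrolled in the treatment phase until Week 8. The SAP does not say which date ends that phase. If it were the last-dose date, 9.2 would reduce to the 13.1 formula.

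The consequence is limited to the supportive per-protocol analyses of the primary and secondary endpoints, the deviation classification and the compliance tables. The ITT primary analysis and the sequential secondary tests are unaffected. It is worth correcting because it is cheap and can change per-protocol membership.

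**What to change.** In SAP 13.1, make the percent-compliance denominator the expected doses over the time enrolled in the treatment phase, as in SAP 9.2:

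- with a Week 8 visit: Week 8 study day minus 1, which is also the count in Protocol 3.3;
- leaving before Week 8: days to exit from the treatment phase, with the exit date defined as something other than the last dose.

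Cite this one figure for the 80% rule in SAP 8 and 9.2. Keep doses over days exposed only as a separately labelled on-treatment descriptive measure. Settle this before unblinding, when per-protocol membership is fixed.

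The cost is a short text change and one derived variable. The downside is that a few subjects who stop drug but remain enrolled move out of the per-protocol set.

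Applying 56 planned doses to everyone, including early leavers, is not recommended as part of this correction. It would remove anyone with fewer than 45 doses, including subjects who stopped for an adverse event or lack of efficacy and count as failures. That selects on outcome and is a separate design choice.
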